## 8 STATISTICAL CONSIDERATIONS

### 8.1 STATISTICAL HYPOTHESES

#### Primary Outcome Measure

Hypothesis: All-cause mortality in patients with an incidental thyroid nodule on PET-CT who did not have thyroid ultrasound within 3 months is no worse than 5% higher than those who did have ultrasound within 3 months.

Null hypothesis: All-cause mortality in patients with an incidental thyroid nodule on PET-CT who did not have thyroid ultrasound within 3 months is more than 5% higher than those who did have ultrasound within 3 months.

## Secondary Outcome Measure(s)

Hypotheses: Incidence rate ratios of (1) thyroid cancer diagnoses, (2) thyroid ultrasounds, (3) thyroid biopsies, and (4) thyroid surgeries are each higher in patients with an incidental thyroid nodule on PET-CT who had versus did not have thyroid ultrasound within 3 months.

Null hypotheses: Incidence rate ratios of (1) thyroid cancer diagnoses, (2) thyroid ultrasounds, (3) thyroid biopsies, and (4) thyroid surgeries are each not  $>1$  in patients with an incidental thyroid nodule on PET-CT who had versus did not have thyroid ultrasound within 3 months.

## 8.2 SAMPLE SIZE DETERMINATION

Informed by a preliminary sample of 84,775 patients undergoing CT and MRI imaging in 2015 with baseline rates of 10-year mortality of 39.5%, covariate adjusted power was assessed via simulation. For each simulated dataset, we resampled sex and age from the empirical covariate distribution among the sample of 84,775 patients and generated a binary indicator of 5- or 10-year mortality from a logistic regression model whose coefficients reflected the actual strength of association between each covariate and mortality. A logistic regression model was then fit to each simulated data set, where the primary coefficient of interest reflected the log odds ratio between treatment and mortality. Covariate adjusted power was calculated as the fraction of simulated datasets for which the two-sided confidence interval for this coefficient did not contain 0.2275, the value of the log-odds ratio corresponding to a 5% non-inferiority margin given the baseline mortality rate of 39.5%. Given that more covariates will be available once final analysis datasets are compiled, this method reflects a conservative estimate. Based on the results we anticipate having at least 75% power for a 5% non-inferiority margin.

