	
Kaplan-Meier to estimate probability of mortality in each arm
 
Construct a 95% confidence interval for the absolute difference between the two arms, <math>\Delta_{RD}</math>
 
Taking the type I error rate, alpha, to be 0.05, non-inferiority is concluded if the upper limit of a two-sided 90% = 100(1-2alpha)% confidence interval for <math>\Delta_{RD}</math> is less than the prespecified margin.
	
baseline; one clone assigned to each treatment strategy.
 
2. Person-time for each clones is censored when their observed treatment strategy is non-adherent. That is, clones assigned to undergo thyroid ultrasound within 3 months are censored at 3 months of follow-up if no ultrasound is performed. Similarly, clones assigned to not undergo an ultrasound within 3 months are censored at the time an ultrasound is performed.
 
3. A pooled logistic regression model is fit for the (conditional) probability of adherence, adjusting for a priori specified baseline factors that predict adherence.
 
4. A marginal structural pooled logistic regression model is fit to the mortality outcome data, as a function of time and treatment (with interaction), using inverse-probability of censoring weights from step 3.
 
5. Treatment-specific marginal probabilities of all-cause mortality are estimated from the fit in step 4, from which the causal risk difference, <math>\Delta_{RD}</math>, is estimated along with a two-sided 90% = 100(1-2alpha)% confidence interval (constructed via the bootstrap).
 
6. Taking the type I error rate, alpha, to be 0.05, non-inferiority is concluded if the upper limit of a two-sided 90% = 100(1-2alpha)% confidence interval for <math>\Delta_{RD}</math> is less than the prespecified margin.

Secondary Outcomes	
Cumulative over 7-years from PET:
 
Number of thyroid cancers
 
Number of thyroid ultrasounds
	
Cumulative incidence rate over 7-years from PET or to the end of the study period

	Number of thyroid biopsies Number of thyroid surgeries	
Exploratory Analysis	Types of thyroid cancer diagnoses	Same

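### The stated power of at least 75% is not the power of the 7-year weighted primary analysis, and its log-odds margin of 0.2275 is not reproduced from the inputs given

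*Combined protocol and SAP*

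**What the plan says.** Section 8.2 takes its planning data from "a preliminary sample of 84,775 patients undergoing CT and MRI imaging in 2015", with "baseline rates of 10-year mortality of 39.5"%. For each simulated dataset, "we resampled sex and age from the empirical covariate distribution", and the simulation then "generated a binary indicator of 5- or 10-year mortality from a logistic regression model". A logistic regression was fitted, and success meant that the interval for the treatment coefficient "did not contain 0.2275, the value of the log-odds ratio corresponding to a 5% non-inferiority margin given the baseline mortality rate of 39.5"%. The section describes the result as covariate-adjusted power. Because more covariates will be available later, it adds that "this method reflects a conservative estimate", and it ends with "we anticipate having at least 75% power for a 5% non-inferiority margin". It gives no number of eligible patients, no share having ultrasound, no confidence level and no covariate coefficients.

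The primary analysis is set out in Section 1.2. Each patient is cloned and the clones are artificially censored. An adherence model supplies weights, and then "A marginal structural pooled logistic regression model is fit to the mortality outcome data" as a function of time and treatment. Non-inferiority is concluded if the upper limit of a two-sided 90% bootstrap interval for the risk difference lies below the margin. Section 4.1 makes that margin an absolute 5 points at 7 years, and Section 8.4.1 also names 7 years. Accrual runs from 1 January 2015 to 31 December 2021 (Section 5.1), and mortality data end on 15 October 2025 (Section 4.3).

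**The concern.** Two things look wrong. First, the conversion of the margin to the log-odds scale does not follow from the two numbers that the sentence gives. Second, the simulated analysis differs from the primary one in horizon, scale, weighting, censoring and source population, and possibly in confidence level.

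Power does not set enrolment here, because every eligible patient is used. It does govern how a failure to show non-inferiority is read: as an imprecise result or as one that counts against omitting ultrasound. A figure presented as a floor, and called conservative, steers that reading. Section 4.1 also allows the margin to be re-evaluated after the secondary results are seen, so the precision expected beforehand should be documented soundly.

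**Working it through.** **1. The margin conversion.** The inputs are 39.5% and 5 points (Section 8.2).

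logit(0.445) − logit(0.395) = −0.2209 − (−0.4263) = 0.2054.

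In reverse, expit(−0.4263 + 0.2275) = 0.4505, a margin of 5.55 points. Other direct readings also miss 0.2275: 5 points downward gives 0.2147, 5 points centred on 39.5% gives 0.2094, the log risk ratio is 0.1192, and a relative 5% gives 0.0820. A 5-point rise equals 0.2275 at a baseline of 30.2%, which the section does not mention.

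**2. Could 0.2275 be conditional?** Odds ratios are non-collapsible, so a covariate-conditional log-odds ratio that yields a 5-point marginal difference exceeds 0.2054. Assume a normal covariate linear predictor with standard deviation s. Solve for a in E[expit(a + sX)] = 0.395, then for b in E[expit(a + b + sX)] = 0.445:

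| s | 0 | 0.5 | 0.7 | 0.8 | 1.0 |
|---|---|---|---|---|---|
| b | 0.2054 | 0.2173 | 0.2278 | 0.2339 | 0.2478 |

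The value 0.2275 is reached at s of about 0.70 (AUC about 0.68). That would be, for example, an age log-odds ratio of 0.35 to 0.46 per 10 years with an age SD of 20 to 15. The documents neither confirm nor exclude it.

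**3. Effect if 0.2275 is marginal.** The 75% cannot be recomputed without N, ultrasound share, confidence level and coefficients. So take it as exactly 75% and hold the implied standard error fixed.

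- 90% interval: SE = 0.2275/(1.645 + 0.674) = 0.0981. Power at 0.2054 = Φ(0.2054/0.0981 − 1.645) = 67%.
- 95% interval: SE = 0.2275/(1.960 + 0.674) = 0.0864. Power at 0.2054 = Φ(0.2054/0.0864 − 1.960) = 66%.
- Keeping 75% would take (0.2275/0.2054)² = 1.23 times the patients.

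**4. Simulated against planned analysis.**

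| | Section 8.2 | Primary analysis |
|---|---|---|
| Horizon | 5 or 10 years | 7 years |
| Measure | logistic log-odds ratio | marginal risk difference |
| Weights | none described | clone-censor weights |
| Censoring | none described | administrative and artificial |
| Interval | level not stated | two-sided 90%, bootstrap |
| Source | CT and MRI patients | PET-CT patients with a nodule |

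Reaching 7 years by 15 October 2025 requires a PET-CT by 15 October 2018. That is 1,383 of 2,557 accrual days, or 54%. For 10 years it is 287 of 2,557, or 11%.

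**5. Moving to a 7-year risk difference, before weighting.** Assumptions: constant hazard, uniform accrual, 1:1 split, no true difference, Kaplan-Meier variance, and exactly 75% power as simulated.

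- Hazard = −ln(0.605)/10 = 0.0503, so 7-year mortality = 1 − exp(−7 × 0.0503) = 29.7%.
- Implied N = 4/(SE² × 0.395 × 0.605), using unrounded SEs: 1,740 if a 90% interval was simulated, 2,245 if 95%.
- Variance per patient without censoring: 0.297 × 0.703 = 0.209. Minimum follow-up of 3.79 years and 54% able to reach year 7 inflate it by 1.175, to 0.245.
- Simulated at 90%: SE = √(4 × 0.245/1,740) = 0.0237; power = Φ(0.05/0.0237 − 1.645) = 68%.
- Simulated at 95%: SE = √(4 × 0.245/2,245) = 0.0209; power at the planned 90% interval = Φ(0.05/0.0209 − 1.645) = 77%.

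In the second case, a net variance inflation from the weights above about 1.06 brings power below 75%.

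**6. The conservative label.** Its only stated reason is that more covariates will be available. In Section 1.2 the outcome model contains time and treatment alone. The extra covariates enter through the adherence weights, so the precision gain of a covariate-adjusted outcome regression does not carry over automatically.

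**The case against.** The strongest reply is that 0.2275 is not a mistake. The section describes covariate-adjusted power and generates mortality from sex and age, so a conditional value is natural, and step 2 reaches 0.2275 with a plausible age effect. This stands: a reader might infer a proven arithmetic error, but the documents show only a value whose derivation is missing. If it is conditional, replacing it with 0.2054 would introduce an error.

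A reader might also infer that power is definitely overstated. The documents do not support that. The 75% is given as a floor, and the simulated confidence level is unknown. If the simulation used 95% intervals, moving to the planned 90% interval gives 84% at 0.2275 and 77% even at 0.2054. The Kaplan-Meier inflation of 1.175 is also somewhat harsh for a pooled logistic model in time. A parametric fit under constant hazard gives about 1.09, and so 71% rather than 68%.

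Nor can one say that the weights must cost precision. Estimated weights containing prognostic covariates can recover some, while strong confounding or a rare exposure can lose it. The net effect depends on data that the documents do not give, so a power figure built on an assumed design effect would be illustration only.

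Finally, Section 8.2 counts any interval that excludes the margin, including one lying wholly above it. With no true difference and 75% power, that has a probability of about 0.00004 and is immaterial.

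None of this makes the simulated analysis the planned one, or supplies the missing inputs.

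**Conclusion.** The point holds in this form: the stated power belongs to an analysis that the study will not run, and it rests on a margin value that its own two inputs do not reproduce. The mismatch in horizon, scale, weighting, censoring and source population is plain from the text.

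The size is conditional. If 0.2275 is marginal, 75% becomes 66% to 67% at the same standard error and confidence level. If it is conditional on sex and age, no correction of the margin is due. On a 7-year risk-difference basis before weighting, under the assumptions in step 5, power is about 68% or 77% according to the simulated confidence level. Any net variance inflation from the weights lowers this, and any gain raises it. The power of the actual analysis cannot be computed from the documents. Neither a definite overstatement nor a definite arithmetic error is established. What is established is that neither the floor of 75% nor the conservative label is supported.

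**What to change.** In Section 8.2:

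1. Rerun the simulation on the analysis in Section 1.2: 7-year risk difference, clone-censor weights, accrual 2015 to 2021 with the 15 October 2025 cut-off, the eligible N and the observed ultrasound share. Count success when the upper limit of the two-sided 90% interval is below 5 points.
2. Report N, ultrasound share, confidence level and assumed mortality, and put the resulting power in place of the present figure.
3. Either correct 0.2275 to 0.2054, or state that it is conditional on sex and age and show its derivation.
4. Delete the statement that the estimate is conservative.

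The cost is a rerun of an existing simulation. The eligible N and the ultrasound share can be counted without looking at mortality, and no extra patients are needed. The downside is that the stated power may become less favourable.

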## 8.3 POPULATIONS FOR ANALYSES

Single dataset for per-protocol analysis including all patients who met the inclusion/exclusion criteria.

## 8.4 STATISTICAL ANALYSES

### 8.4.1 GENERAL APPROACH

For descriptive statistics, categorical data will be presented, stratified by observed treatment status, as percentages while continuous data will be presented as medians and interquartile ranges. For non-inferiority (primary aim) inferential tests, statistical significance is defined as the estimated 7-year mortality two-sided confidence interval of the study group not crossing an absolute 5% lower 7-year mortality rate of the reference group. For superiority (secondary aims) inferential tests, statistical significance is defined as the estimated between-group difference two-sided confidence interval not crossing zero.

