## 4 STUDY DESIGN

### 4.1 OVERALL DESIGN

We hypothesize that all-cause mortality in patients with an incidental thyroid nodule on PET-CT who did not have thyroid ultrasound (the exposure) within 3 months of the PET-CT is non-inferior within a 5% margin to those who have thyroid ultrasound at 7-years. That is, among patients with an incidental thyroid nodule on PET-CT, mortality is no more than 5% larger (in absolute difference) for those who do not have thyroid ultrasound compared to those who do. We will also report mortality differences at landmark timeframes of 1-year, 3-years, 5-years, and 10-years.

Understanding an expected 30%-50% baseline 10-year mortality rate in patients who undergo PET imaging at our institution, a 5% non-inferiority margin was chosen based on the most conservative proposed margin by 2 thyroid endocrinologists (one did not respond) and a head and neck surgeon (other proposed margins were 7% and 10%). This margin decision was informed by typical margins of 5% to 10% used in non-inferiority trials of medications with outcomes involving mortality and by recent non-inferiority trials of thyroid cancer treatments. The observational nature of this non-inferiority study and absence of prior studies that show effect sizes for the reference make ideal margin point-estimate and fixed-estimate calculations impossible, but our expert panel method is supported as a practical necessity to provide guidance on the fraction of the point estimate of the active comparator that stakeholders are willing to lose at a cost of gaining other advantages (in this case, likely fewer biopsies and surgeries), as in the point-estimate margin calculation method. Given this careful pre-specification of our margin with this panel decision, we will follow published methodology recommendations and consider re-evaluation of the margin based on the secondary benefits seen in the emulated trial or we may conduct the final analysis without reference to a margin. These decisions will be clearly detailed in final manuscripts.

To estimate group differences in mortality, we will conduct a non-inferiority emulated target trial utilizing clone-censor weighting to address potential immortal time bias introduced by the 3-month grace period. We will adjust for all variables labeled as demographic, potential confounder, or mortality risk adjustor in as listed in the Section 7, below.

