## 4.2 SCIENTIFIC RATIONALE FOR STUDY DESIGN

The baseline 10-year mortality of patients undergoing PET examinations at our institution are in the range of 30%-50%. Our interest is in whether, following the detection of a thyroid nodule, doing nothing (i.e. no thyroid ultrasound) results in mortality that is no worse than 5% more than doing something (i.e. thyroid ultrasound). Thus we are using a non-inferiority design. Since performing an ultrasound aligns with ACR recommendations, we've designated the imaged group as the reference group.

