#### 8.4.3 ANALYSIS OF THE PRIMARY OUTCOME MEASURE(S)

The statistical analysis plan is outlined in detail in the Target Vs. Emulated Trial Table in Section 1.2. We do not anticipate substantive missing data.

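### Section 8.4.1 puts the non-inferiority boundary 5 points below the reference mortality and tests one arm's interval against it, so a clearly harmful result would satisfy it

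*Combined protocol and SAP*

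**What the plan says.** The plan gives two decision rules for the primary endpoint.

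- **Section 8.4.1 (General Approach)** defines statistical significance for the primary aim as "the estimated 7-year mortality two-sided confidence interval of the study group not crossing an absolute 5% lower 7-year mortality rate of the reference group". It calls the interval two-sided but gives no confidence level.
- **Section 1.2 (Target vs. Emulated Trial Table)** works with the between-arm risk difference and a bootstrap interval: "non-inferiority is concluded if the upper limit of a two-sided 90% = 100(1-2alpha)% confidence interval for" that difference lies below the prespecified margin. Alpha is 0.05.

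The other sections fix the roles of the arms and the direction of the margin.

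- **Section 4.2:** "we've designated the imaged group as the reference group". The study group is therefore the no-ultrasound arm.
- **Section 4.1:** the claim to be supported is that "mortality is no more than 5% larger (in absolute difference) for those who do not have thyroid ultrasound compared to those who do".
- **Section 8.1:** under the null hypothesis, mortality without ultrasound "is more than 5% higher than those who did have ultrasound within 3 months".
- **Section 8.4.3**, on the primary outcome, refers back: "The statistical analysis plan is outlined in detail in the Target Vs. Emulated Trial Table in Section 1.2".

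**The concern.** The 8.4.1 sentence differs from the rest of the plan in three ways.

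1. **Direction.** It places the boundary at reference mortality minus 5 points. The hypothesis, the null and the margin all concern reference mortality plus 5 points.
2. **Form.** It compares the interval for one arm's mortality with the other arm's rate. The reference arm's sampling error drops out, so even a correctly directed version would not hold alpha at 0.05.
3. **Level.** It names no confidence level. Section 1.2 uses 90% for the primary decision, and Section 8.4.4 uses 95% for secondary outcomes.

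The direction matters most. An interval that does not cross a value lies wholly above it or wholly below it. The further no-ultrasound mortality rises above the reference, the more surely its interval clears a boundary set below the reference. The rule therefore does not test the null in Section 8.1, and it is easiest to meet when omitting ultrasound does harm. The same data could be reported as non-inferior under 8.4.1 and as failing under 1.2.

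**Working it through.** **Inputs from the plan.** Margin 5 points absolute (4.1); alpha 0.05 through a two-sided 90% interval (1.2); baseline mortality 39.5% at 10 years in a CT/MRI sample, and anticipated power of at least 75% (8.2).

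**Assumptions.** The plan gives no sample size, arm shares, 7-year mortality or assumed true effect, so the 75% power cannot be reproduced and is used only to set a plausible scale. The arms are treated as independent with a normal approximation. Cloning and weighting are ignored. Because 8.4.1 gives no level, 90% is used unless stated.

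**Notation.** d = true risk difference, no ultrasound minus ultrasound; SE = standard error of the estimated difference; s = standard error of the no-ultrasound mortality alone; Φ = standard normal distribution function.

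- Section 1.2 rule: P = Φ((0.05 − 1.645·SE − d)/SE)
- Section 8.4.1 as written: P = [1 − Φ((−0.05 + 1.645·s − d)/SE)] + Φ((−0.05 − 1.645·s − d)/SE)
- Section 8.4.1 with only the direction corrected: P = Φ((0.05 − 1.645·s − d)/SE)

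**Step 1: the plan's own alpha.** At d = 0.05 the Section 1.2 rule gives Φ(−1.645) = 5.0%, as intended.

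**Step 2: scale.** For 75% power at d = 0 with a 90% interval, SE = 0.05/(1.645 + 0.674) = 0.02156, or 2.16 points. If the ultrasound arm holds a share q of patients and the arms have equal variance per patient, s = SE·√q. This gives s = 0.0152 at q = 50% and s = 0.0096 at q = 20%.

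**Step 3: probability of declaring non-inferiority.**

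| True d | 8.4.1 as written, q = 50% | 8.4.1 as written, q = 20% | Section 1.2 rule |
|---|---|---|---|
| −5 points | 24% | 46% | 99.9% |
| 0 | 88% | 94% | 75% |
| +5 points (null boundary) | >99.9% | >99.9% | 5.0% |
| +10 points | about 100% | about 100% | <0.1% |

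Worked entry, q = 50% and d = +0.05: (−0.05 + 1.645 × 0.01525 − 0.05)/0.02156 = −3.47, and 1 − Φ(−3.47) = 99.97%. The second term is negligible.

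**Step 4: sensitivity.** With explicit binomial arms, a 39.5% reference rate and 1,042 patients per arm, the literal rule gives 99.97% at +5 points, 88% at 0 and 25% at −5 points. Simulation with 200,000 replicates agrees. The probability at +5 and +10 points stayed above 99% in every setting tried: 90% or 95% intervals with 1,042 per arm, 500 reference to 2,000 study, and 300 to 2,700; and reference rates of 20%, 30% and 50% with 1,000 per arm and a 90% interval.

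**Step 5: one dataset, two verdicts.** Take observed mortality of 49.5% without ultrasound and 39.5% with it, 1,042 per arm.

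- s = √(0.495 × 0.505/1042) = 0.0155, so the no-ultrasound 90% interval is 47.0% to 52.0%. The 8.4.1 boundary is 39.5% − 5% = 34.5%. The interval does not cross it, so the rule is met.
- SE = √(0.0155² + 0.0151²) = 0.0217, so the 90% interval for the difference is +6.4 to +13.6 points. The upper limit exceeds 5, so Section 1.2 does not conclude non-inferiority. The whole interval lies above the margin.

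**Step 6: is changing one word enough?** No. With the boundary moved to 5 points higher but the one-arm interval kept, the error rate at d = +5 points is 12.1% (90% interval, 1,042 per arm), 8.1% (95%, same arms), 22.8% (90%, 500 reference to 2,000 study) and 29.9% (90%, 300 to 2,700), against a nominal 5%.

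**The case against.** The strongest reply is that Section 8.4.3, the section on the primary outcome, sends the reader to Section 1.2, where a complete two-arm rule with its level is set out. Section 8.4.1 is only a general introduction. The synopsis and Sections 4.1, 4.2 and 8.1 all give the direction as higher mortality without ultrasound, and the power margin in 8.2 is a positive log-odds ratio. On this view the sentence is a slip, perhaps written with survival in mind, and an analyst following 8.4.3 would do the right thing. One can also strain the sentence to mean that the reference rate is 5% lower than the study rate, which restores the direction.

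Much of this stands. The sentence is probably a drafting error, and the plan does not show that the primary analysis will be run wrongly. The numerical illustration also rests on assumed arm shares, an assumed standard error and independent arms, so the 88% to 94% and 24% to 46% figures are not properties of this study.

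It does not clear the sentence. Section 8.4.1 is where significance for the primary aim is defined, and no text says that Section 1.2 prevails over it. The strained reading leaves the one-arm interval, with error rates of 12% to 30% at the margin under a 90% interval in the allocations tried. Section 4.1 also leaves open re-evaluating the margin or analysing without one, so an unambiguous prespecified rule matters more here.

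**Conclusion.** The concern holds. As written, the 8.4.1 criterion contradicts the null hypothesis in 8.1, the margin in 4.1 and the decision rule in 1.2. It would be met almost surely at and beyond the degree of harm the study is meant to exclude. The direction error and the one-arm comparison follow from the text alone. The probabilities depend on the assumptions listed, but the result at +5 and +10 points stayed above 99% throughout. The defect lies in the stated rule and is not evidence of a planned misanalysis. Because it concerns the success criterion for the only primary endpoint, it must be corrected before analysis.

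**What to change.** Replace the non-inferiority sentence in Section 8.4.1 with the Section 1.2 rule, for example: *Non-inferiority is concluded if the upper limit of the two-sided 90% bootstrap confidence interval for the 7-year risk difference (no ultrasound minus ultrasound) is below +5 percentage points.* Delete the single-arm wording altogether; changing lower to higher would not be enough.

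The sign convention in parentheses is an addition, because Section 1.2 does not say which arm is subtracted from which. State it there too, so that the two sections match.

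The cost is one sentence in 8.4.1 and a short clarification in 1.2. No data, design or computation changes.
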